Extensive research in animal models has shown a benefit to using intravenous (IV) vitamin C in sepsis.^{4,5} It is a cofactor for multiple enzymatic functions.⁶ In addition, one study in particular found that critically ill patients, including those with sepsis have significantly lower levels of circulating vitamin C during their acute illness than their healthy counterparts. Furthermore, the investigators found critically ill patients who were administered an infusion of vitamin C every six hours maintained normal plasma levels for the largest amount of time.⁶ One study showed that critically ill patients required up to 3 grams per day of vitamin C just to return their plasma concentrations to normal baseline levels.⁷ Additional research indicates that critically ill patients are often thiamine-deficient which is frequently missed and not treated by their clinicians.^{8,9}

Marik et al. published a novel study implicating the use of IV vitamin C, vitamin B₁, and hydrocortisone resulted in a significantly lower mortality rate for their septic patients. His team explored the utility of these medications as compared to historical controls of their previously treated septic patients.¹⁰ This study, while novel and inspiring, was designed with the acceptance of multiple confounders and potential for bias including the retrospective nature, the lack of randomization, and the lack of blinding. We propose investigating the use of IV vitamins B₁ and C in a randomized, prospective trial, eliminating the potential for selection bias.

Hypotheses

[figure not shown]
1. Primary Hypothesis: Septic patients in the ICU who receive IV vitamins B₁ and C will demonstrate a decreased mortality rate compared to septic patients who do not receive IV vitamins B₁ and C.
2. Secondary Hypotheses: Patients receiving IV vitamins B₁ and C
 - a. will have shorter hospital length of stays (HLOS)
 - b. will have shorter ICU length of stays (ICU LOS)
 - c. will demonstrate a lower 30-day readmission rate
 - d. will have fewer ventilator days
 - e. will have fewer hours on vasopressors
 - f. in addition to IV hydrocortisone for refractory septic shock will have a more profound reduction in mortality when as compared to those receiving IV vitamins B₁ and C alone

g. who also record to higher Sequential Organ Failure Assessment (SOFA) scores will have a more significant reduction in mortality than patients who record lower SOFA scores

Objectives

The objective of this study is to determine if the administration of IV vitamins B₁ and C are effective in decreasing the mortality rates of patients with severe sepsis or septic shock. In addition, we will investigate if there are benefits to those patients who also receive hydrocortisone in an effort to explore the synergistic relationship that vitamins B₁ and C have with hydrocortisone.

Overview of Study Design

Patient Selection Criteria

1. Inclusion Criteria: Patients admitted to the ICU at Saint Francis Hospital and Medical Center who are:
 - a. Between the ages of 18 and 90 years old
 - b. Have severe sepsis or septic shock
 - i. Severe sepsis and septic shock will be defined by the Surviving Sepsis 2012 guidelines¹¹
 - c. Weight more than 30 kg
 - d. Full code
2. Exclusion Criteria: Patients
 - a. Not diagnosed with severe sepsis or septic shock
 - b. Younger than 18 or older than 90 years old
 - c. Who are pregnant
 - d. Weigh less than 30 kg

- e. Currently on hemodialysis
- f. Not located in the ICU
- g. Do not resuscitate (DNR) or do not intubate (DNI), no escalation of care, or comfort measures only (CMO)

Enrollment/Randomization

Once identified, patients who meet inclusion criteria will be approached. The majority of patients are likely to be intubated and sedated at the time of their diagnosis of severe sepsis or septic shock. In these cases, the next of kin or consenting party will be approached for each patient. The providers in the ICU, mainly physician's assistants (PAs) and residents, always contact patient's family members for consent for central lines and other invasive procedures while in the ICU. The study staff will speak to this same consenting person (in person or on the phone) and will ask them about the potential enrollment of their loved one in the study. In the absence of documentation of a healthcare proxy or conservator (as is often the case with septic patients, as it is an unexpected illness), priority will be given to the patient's spouse, followed by an adult child, followed by a parent, followed by an adult sibling. .

Due to the impact of the COVID-19 pandemic and associated restrictions and worry, it has been increasingly challenging to provide informed consent *in person* with legally authorized representatives. Hospital restrictions combined with a general reluctance of LAR's desire to come to the hospital and risk exposure makes in-person consent problematic. Consent will be obtained via one of two methods: (1) obtained in-person and documented by double signature, or (2) obtained telephonically with an additional hospital signatory witness. The research team will then memorialize written consent by post (mail) or electronic mail, when possible, but telephonic consent will be sufficient for recruitment of subjects and protocol start. If the consenting party is only available via phone, the study will be discussed with this Legally Authorized Representative, and additional family member as desired, thoroughly, and the research staff will then return a call at a reasonable interval, usually in two hours, to respond to any questions. Questions provided immediately will be answered in real time. During the two hour interval, the consent form will be faxed or emailed to the legally authorized representative for review. This telephonic consent will be witnessed by another member of the hospital team to ensure that the study is clear to the family member and all questions have been answered. We will then randomize the patient and begin treatment. If and when the subject has regained the mental capacity to participate in the informed consent process, s/he will be approached by the research staff and consented clarified. If the patient does not continue consent, they will be withdrawn from the study.

Prior to the recruitment process the pharmacy will enter numbers 1-120 in ascending order into a randomizing website. This randomly assigned each number to either placebo or intervention. Prior to recruitment, kits in blocks of 10, containing either the placebo or unmixed forms of vitamin B₁ and C are made and placed in identical packages labeled with their corresponding number. These numbers will be assigned in ascending order corresponding to the order in which they are consented. Once ordered by the providers the pharmacy will open the identical kits and, if it is the intervention, mix the vitamin B₁ and C for IV administration. This process will ensure the study coordinators, healthcare providers, and the patients remain blinded. Vitamins B₁ and C will be ordered for all patients in Epic, giving the impression that all of those

enrolled are in the intervention group. However half the kits will contain the intervention and half will contain the placebo. This is being done due to logistical issues with preparing and storing the vitamin B₁ and C. Having premade kits allows the pharmacy to more easily prepare and distribute the vitamin B₁ and C. These also need to be refrigerated and given limited space kits will be made in blocks of 10 to limit crucial storage space the pharmacy needs for other medications.

We plan to enroll 120 patients; 60 in the control arm and 60 in the intervention arm. Our current mortality rate is 35% at Saint Francis Hospital and Medical Center for patients with severe sepsis and septic shock. We expect our mortality rate to decrease to 30% with this intervention. We believe this is a reasonable expectation given that Marik et al. demonstrated that his intervention group's mortality rate dropped from 40.4% to 8.5% after a similar intervention.¹⁰ In order to demonstrate this difference, 120 patients are needed according to our power calculation.

Informed Consent/Ethical Issues

We anticipate a full board IRB approval, as this is a prospective study involving vitamins B₁ and C as the intervention. Appropriate patients will be approached and consented (often via proxy consent) by members of the research team. Patients will then be randomized by computer to receive vitamin C and vitamin B₁, or normal saline (control). The treating physicians, the research team, and the patients will all be blinded. The pharmacist mixing the drugs will be the only non-blinded team member.

Data will be kept on an encrypted, password-protected computer behind two locked doors. Data will be managed by the investigators who will each have their own login.

Study Workflow

Patients admitted to the ICU who have severe sepsis or septic shock will be identified by the nursing staff, PAs, or physicians caring for them. These patients' consenting party will be approached within 24 hours of their presentation to the ED in an attempt to obtain informed consent. Following consent, the pharmacy will be notified of the study patient, randomization will occur, and the mixed medications (control or intervention) will be delivered to the patient's bedside in the ICU. Consented patients will receive 1.5g of vitamin C in 100mL of 0.9% sodium chloride (normal saline) every six hours for four days or until discharge from the ICU, whichever happens first (seventeen dose maximum). In addition, they will receive 200 mg IV vitamin B₁ every 12 hours in 100 mL of normal saline for four days or until ICU discharge (whichever happens first, nine dose maximum). Patients in the control arm will receive the 100 mL of 0.9% sodium chloride every six hours and 100 mL of 0.9% sodium chloride every 12 hours to act as placebos for the vitamin C and B₁ respectively. Doses up to 200 mg/kg/day were found to be safe in humans in one study.⁶ Several studies have been conducted in human subjects using IV vitamin B₁ and C, often at higher doses than proposed here, and have not seen serious side effects.^{10,12-14}

Some patients may receive hydrocortisone IV for refractory septic shock outside of this study protocol. This will be at the discretion of the treating physician and will not be included in the randomized and blinded intervention. Hydrocortisone has been shown in some studies to help

in patients with refractory septic shock.^{15,16} However, it is not uniformly employed. Patients receiving hydrocortisone will undergo a subgroup analysis to better elucidate the synergistic effects of hydrocortisone with vitamins B₁ and C.

After discharge, patients will be followed for 30 days to track hospital readmissions.

Reporting of Adverse Events

The study personnel will report adverse events as soon as they become aware of them and within 24 hours of them being informed. All adverse events or unanticipated problems will be reported to the IRB. If the adverse event is thought to be related to the intervention, the medication will be stopped and the patient will be withdrawn from the study. They will be monitored closely for resolution of the adverse event. In order to ensure that the patient receives the ideal treatment for their adverse reaction and their newly-discovered allergy is documented appropriately, the research staff will un-blind the ICU staff and themselves. This will be accomplished by keeping duplicate sealed randomization envelopes. In the case of an adverse event, the research staff will open this additional envelope and inform the treating physicians.

Side Effects

Possible side effects for patients receiving IV vitamin C include diarrhea, nausea, vomiting, heartburn, headache, insomnia, and nephrolithiasis. Possible side effects for patients receiving IV vitamin B₁ include nausea, hives, wheezing, or angioedema. In the event of these reactions, the patients will be treated immediately for their allergic reaction by the primary team and will be withdrawn from the trial as previously mentioned.

Study Withdrawal

All patients who have a serious adverse event thought to be directly related to the intervention will be withdrawn from the study. The patient or their consenting proxy may revoke consent and withdraw from the study at any point as participation is completely voluntary.

Statistical Issues

The intervention arm (vitamin B₁ and C) and the control arm (sodium chloride 0.9%) will be compared statistically for demographics and patient characteristics; including age, gender, comorbidities, need for operative intervention, enteral nutrition, and Body Mass Index (BMI). Outcomes between these two groups will also be compared including hours of vasopressor use, ventilator days, HLOS, ICU LOS, comorbidities, renal function measured by patients' GFR and creatinine levels, procalcitonin levels, SOFA scores, discharge destination, readmission rates, and mortality rates. We will do a subgroup analysis of patients with septic shock as compared to those with severe sepsis. We will also do a subgroup analysis of the patients who receive hydrocortisone as opposed to those who do not.

Fisher's exact test will be used to compare gender, operative intervention, rate of mortality and the 30-day readmission rate. Average BMI and average age will be evaluated via student's t-

test. Median number of ventilator days, average hours of vasopressor use, median daily SOFA scores, average procalcitonin levels, average creatinine levels, median GFR, median ICU LOS and median HLOS will all be compared via Mann-Whitney U test. A contingency table will be used to analyze the different types of enteral nutrition and patients' discharge destination. A multivariate regression analysis will be conducted to analyze patients' comorbidities.

Duration of Review

We will start recruiting patients on September 10, 2018. We expect recruitment and data collection to take 12 months. Data analysis and completion of a manuscript is expected to take another 12 months.

All data will be kept on a password-protected and encrypted computer located behind two locked doors. We will retain all data for three years after the completion of the study. Following this, all data will be deleted from the hard drive where they will be kept.

Publication Plan

We plan to write and submit a manuscript for publication in a peer-reviewed journal.

References

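### Allocation is not stratified by septic shock and the mortality test is not adjusted for it, so chance imbalance on the main severity split is neither prevented nor corrected

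*Combined protocol and SAP*

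**What the plan says.** The combined protocol and SAP describes allocation under Enrollment/Randomization. "Prior to the recruitment process the pharmacy will enter numbers 1-120 in ascending order into a randomizing website". The result of that step is described in a single sentence: "This randomly assigned each number to either placebo or intervention". The algorithm is not given: simple randomisation, a shuffled list with fixed totals and permuted blocks would all fit that sentence. The section adds that half the kits are active and half placebo, and gives the target: "We plan to enroll 120 patients; 60 in the control arm and 60 in the intervention arm". Numbers are issued from a single ascending list as patients are consented, so shock status plays no part.

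The only blocks mentioned are kit batches: "Prior to recruitment, kits in blocks of 10, containing either the placebo or unmixed forms of vitamin B₁ and C are made". The reason given is refrigerator space: "given limited space kits will be made in blocks of 10 to limit crucial storage space". Whether each batch holds five active and five placebo kits is not stated.

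The inclusion criteria require severe sepsis or septic shock under a named guideline, so the distinction is available before randomisation. Statistical Issues uses it only for a subgroup: "We will do a subgroup analysis of patients with septic shock as compared to those with severe sepsis". Mortality is assigned Fisher's exact test with no covariate. The one regression named is for comorbidities; its outcome is not stated and shock is not mentioned.

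**The concern.** Shock is the clearest severity split in this population, and the plan treats it as important enough for a subgroup analysis. In a trial of 120, a single unstratified list will often leave the arms with different proportions in shock. An unadjusted test then carries that difference into the mortality comparison. The effect sought is only 5 points (35% to 30%), so a shift of a few points from case mix alone would make the estimate harder to read. The shock subgroup could also end up with uneven arms. Adjusting for a factor recorded at entry removes this component of noise at almost no cost.

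**Working it through.** **Inputs from the documents (Enrollment/Randomization):** 120 patients, 60 per arm, mortality 35% versus 30%. **Assumed, because the documents do not give them:** share in shock q = 40-60%; shock minus non-shock mortality gap D = 20 or 30 points, with 10 shown for range.

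**1. The plan's own figure.** The 60:60 split follows if exactly half of 120 kits are active. The claim that 120 patients suffice does not reproduce. With two-sided 5% and 80% power (assumed; neither is stated), n per arm = [1.96√(2·0.325·0.675) + 0.842√(0.35·0.65 + 0.30·0.70)]² / 0.05² ≈ 1,377. With 60 per arm, two-sided power is 8.4% by normal approximation and 6.0% for Fisher's test. This sets the scale for what follows.

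**2. Shock imbalance with exactly 60:60.** Let S of the 120 patients have shock, with X of them in one arm. X is hypergeometric with variance 60·q(1−q)·(60/119), and the between-arm difference in shock proportion is (2X − S)/60.

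- q = 50% (S = 60): variance 60·0.25·0.504 = 7.56, SD(X) = 2.75, SD of the difference = 2·2.75/60 = 9.2 points.
- q = 40% or 60%: SD of the difference = 9.0 points.
- P(difference of 10 points or more) = 36% at q = 50% and 35% at 40% or 60%.
- At q = 50%, P(shock subgroup splits 35:25 or worse) = 10%.
- Unstratified permuted blocks of 10 also give 36% at q = 50%. Blocking alone does not address shock imbalance.

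**3. Shift in the crude mortality difference.** Shift = imbalance × D, so its 95% range is ±1.96 × SD × D. With q = 50%:

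| D (points) | 95% range of shift (points) | P(shift of 2.5 or more) | P(shift of 5 or more) |
|---|---|---|---|
| 10 | 1.96·0.0917·10 = ±1.8 | 0.6% | about 0 |
| 20 | 1.96·0.0917·20 = ±3.6 | 20% | 0.6% |
| 30 | 1.96·0.0917·30 = ±5.4 | 36% | 10% |

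At q = 40% or 60% the ranges for D = 20 and 30 are ±3.5 and ±5.3.

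**4. What adjustment recovers.** At the mean mortality of 32.5%, the unadjusted SE of the difference is √(2·0.325·0.675/60) = 8.6 points. Using the strata removes q(1−q)D² from the outcome variance of 0.2194. At q = 50%:

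- D = 20: √(2·(0.2194 − 0.0100)/60) = 8.4 points.
- D = 30: √(2·(0.2194 − 0.0225)/60) = 8.1 points.

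The parts add up: for D = 20, 8.35² + 1.83² ≈ 8.55². The shock component is already inside the 8.6-point SE and is a small part of it.

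**5. Arm sizes.** A fixed half-and-half list gives 60:60 once all 120 numbers are used. If such a list stopped at 80 (an illustrative figure), exact balance would have probability 15% and one arm would hold 35-45 patients (95% range). Under simple randomisation of 120, P(exactly 60:60) = 7.3% and the 95% range is 49-71. The loss is small either way: a 50:70 split keeps 4·50·70/120² = 97% of the efficiency.

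**The case against.** The strongest reply is that randomisation already accounts for this. Chance imbalance does not bias the estimate or inflate type I error, and it is included in the SE. That is correct. The case for adjustment is precision and readability, and the gain is a few tenths of a point in an SE of 8.6. The more serious weakness in the same section is the sample size, which neither stratification nor adjustment repairs.

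A second reply is that the mortality gap and the share in shock are both assumed. That also stands. At a 20-point gap, a shift as large as the 5-point effect occurs in fewer than 1 trial in 100; it takes a gap of about 30 points to reach 9-10%. A reader might infer that imbalance will commonly match the effect sought. The documents give no figure to support that.

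A reader might also infer that each number is assigned independently and that the 60:60 split therefore fails. The text does not say independently, and its statement that half the kits are active fits a fixed 1:1 list. What can be said is that the algorithm is unstated and that balance is not assured if enrolment stops before 120.

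Finally, recruitment ran into the pandemic, since the consent text addresses COVID-19, whereas Duration of Review says "We expect recruitment and data collection to take 12 months" from September 2018. It is tempting to conclude that case mix drifted and that the arms are unbalanced over time. The documents contain no evidence of changed case mix or mortality, so this remains a possibility only.

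None of these replies supplies a reason to leave shock out of the mortality analysis.

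**Conclusion.** The point holds as a modest, inexpensive improvement. No stratification by shock is stated, and the named mortality test makes no adjustment for it. If 40-60% of patients have shock, about a third of trials run this way (35-36%) would show an arm difference of 10 points or more in shock proportion. The added 95% shift in mortality is about ±3.6 points for a 20-point gap and ±5.4 points for a 30-point gap. These sizes rest on the assumed share and gaps and on exactly 60 per arm. The finding is one of avoidable noise. It does not show bias, a failed 60:60 split, or that the batches of 10 are certainly not randomisation blocks; they are described only as storage batches, so their composition is open.

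**What to change.** Before unblinding, amend Statistical Issues so that the primary mortality comparison is stratified by or adjusted for septic shock versus severe sepsis, as classified at consent. Status later in the stay should not be used, since treatment could affect it. Suitable choices are a Mantel-Haenszel risk difference with an exact or Cochran-Mantel-Haenszel test, or logistic regression with shock as a covariate. The risk difference has the advantage of staying on the scale of the 5-point target. At 32.5% mortality about 39 deaths are expected (0.325 × 120), enough for one binary covariate. Keep Fisher's exact test as a sensitivity analysis.

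In Enrollment/Randomization, state the algorithm that the website used and whether each batch of 10 kits is balanced.

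The cost is a few sentences and one baseline variable that eligibility and the planned subgroup already require. Stratified permuted blocks by shock status are optional, and only if kits for the remaining numbers have not been made. Their price is a second allocation scheme partway through the trial, some extra kit storage and occasional stratum misclassification, and the documents do not show how many numbers remain.

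### 120 patients do not follow from the stated 35% to 30% mortality difference: assuming a two-sided 5% level, 60 per arm gives about 6% power, and 80% power would need about 2,750 to 2,830 patients

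*Combined protocol and SAP*

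**What the plan says.** All the sizing information is in one paragraph of the combined protocol and SAP, under Enrollment/Randomization:

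- Size: "We plan to enroll 120 patients; 60 in the control arm and 60 in the intervention arm".
- Control rate: "Our current mortality rate is 35% at Saint Francis Hospital and Medical Center for patients with severe sepsis and septic shock".
- Expected rate on treatment: "We expect our mortality rate to decrease to 30% with this intervention".
- Support for that expectation: it is introduced with "We believe this is a reasonable expectation given that", followed by a published before-after study in which the "mortality rate dropped from 40.4% to 8.5% after a similar intervention".
- Conclusion: "In order to demonstrate this difference, 120 patients are needed according to our power calculation".

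Lower mortality is the primary hypothesis (Hypotheses, item 1): treated patients "will demonstrate a decreased mortality rate compared to septic patients who do not receive IV vitamins". Under Statistical Issues, Fisher's "exact test will be used to compare gender, operative intervention, rate of mortality and the 30-day readmission rate". The document gives no significance level, sidedness, target power, sample size formula or allowance for withdrawals, and no other reason for enrolling 120.

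**The concern.** A 5-point difference between two mortality rates near one third is small, and detecting it normally takes patients in the thousands. A claim that 120 are enough is therefore suspect on sight. It matters because this sentence is the only justification for the size of the trial, and it concerns the primary outcome.

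A reader who trusts it would take a non-significant result as evidence against the effect the trial was said to be sized to show. If the true rates are 35% and 30%, that reading would nearly always be mistaken: the planned test misses significance in about 94% of such trials, and in about 25% of them the vitamin arm has more deaths than the control arm.

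**Working it through.** **Inputs from the plan.** p1 = 0.35, p2 = 0.30, difference d = 0.05, n = 60 per arm, 1:1 allocation, Fisher's exact test.

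**Inputs I had to assume.** Two-sided alpha 5% (one-sided also shown), 80% power as the benchmark, no dropout.

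**Step 1. Try to reproduce 120.** The usual two-proportion formula per arm, with p̄ = (0.35 + 0.30)/2 = 0.325, is

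n = [z_α √(2p̄(1 − p̄)) + z_β √(p1(1 − p1) + p2(1 − p2))]² / d²

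Here √(2 × 0.325 × 0.675) = 0.6624 and √(0.2275 + 0.2100) = 0.6614.

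- Two-sided 5%, 80% power: (1.960 × 0.6624 + 0.8416 × 0.6614)² / 0.0025 = (1.2982 + 0.5567)² / 0.0025 = 1,376.3, so 1,377 per arm and 2,754 in total.
- With continuity correction, n′ = (n/4)[1 + √(1 + 4/(n d))]² = 1,416.0, so 1,417 per arm and 2,834 in total.
- One-sided 5%, 80% power: (1.645 × 0.6624 + 0.5567)² / 0.0025 = 1,084.0, so 2,168 in total (2,248 corrected).

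Other routes give the same picture:

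| Setting for 35% vs 30% | Total N |
|---|---|
| Unpooled variance, two-sided 5%, 80% | 2,748 |
| Arcsine, two-sided 5%, 80% | 2,752 |
| Two-sided 5%, 90% (corrected) | 3,684 (3,764) |
| One-sided 20%, 50% power | 250 |
| One-sample test against a fixed 35%, one-sided / two-sided 5%, 80% | 548 / 698 |

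None yields 120. The shortfall is 2,754/120 ≈ 23-fold two-sided and 2,168/120 ≈ 18-fold one-sided. Because the planned test is Fisher's, the upper end of the range applies: its exact power is 78.9% at 2,754 patients and 80.0% at 2,832.

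**Step 2. Power at 60 per arm.** I enumerated all 61 × 61 possible tables, weighted each by its binomial probability, and summed those with Fisher p ≤ 0.05.

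| True rates | Fisher power |
|---|---|
| 35% vs 30%, two-sided 5% | 6.0% (5.7% in the favourable direction) |
| 35% vs 30%, one-sided 5% | 10.5% |
| 35% vs 20%, two-sided 5% | 37.5% |
| 35% vs 15%, two-sided 5% | 65.2% |
| 35% vs 13%, two-sided 5% | 75.8% |
| 35% vs 12%, two-sided 5% | 80.6% |
| 35% vs 14%, one-sided 5% | 81.0% |

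The uncorrected normal approximation is a little kinder for 35% vs 30%: 8.4% two-sided and 14.4% one-sided.

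**Step 3. What the expected result would look like.** If deaths match the assumption exactly, the arms have 0.35 × 60 = 21 and 0.30 × 60 = 18 deaths. Fisher p = 0.70. The Wald 95% interval for the reduction is 5 ± 1.96 × √(0.4375/60) × 100 = 5 ± 16.7, or −11.7 to 21.7 points. Over all non-significant tables at these rates, about 97% have a Wald interval that still includes a 5-point reduction. About 94% exclude the cited 40.4 − 8.5 = 31.9-point fall.

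**Step 4. The other reading.** Putting 40.4% and 8.5% into the same formula (two-sided 5%) gives 27.3 per arm (33.3 corrected), so 56 to 68 in total for 80% power. For 90% power it gives 74 to 86. At 60 per arm Fisher power is 98.3%. This reading does not lead to 120 either.

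**The case against.** The best defence is that *this difference* comes straight after the before-after figures, so it might mean 40.4% to 8.5%. On that reading the trial is not underpowered, since 60 per arm has about 98% power. But those figures are brought in only to support 30% as a reasonable expectation, so the natural reading is 35% to 30%. Nor does the other reading rescue the sentence: it leaves 120 unexplained and contradicts the expectation stated just before. What stands is that the charge of low power belongs to the 35% to 30% reading only.

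A second point is that alpha, sidedness and the 80% benchmark are mine. The primary hypothesis is directional, so the one-sided figures are a fair alternative. They change the size of the gap but not the conclusion.

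Third, a single-centre trial may choose 120 for practical reasons. That would be legitimate, but the plan attributes the number to a power calculation.

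Fourth, recruitment was due to start in September 2018 and the consent text mentions COVID-19, so a correction may come after much of the enrolment. That limits what it can achieve, but the result will still be interpreted against this sentence.

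**Conclusion.** The concern holds and needs correcting. On its plain reading, the statement that 120 patients are needed to demonstrate a fall from 35% to 30% is wrong. Power is about 6% (two-sided 5% assumed) or 10.5% (one-sided 5% assumed), and 80% power needs about 2,750 to 2,830 or 2,170 to 2,250 patients respectively. All these figures assume 1:1 allocation and no dropout; withdrawals would lower the power further. The trial can still speak to very large effects, of the order of 35% to 12%, but not to the effect the plan says it expects.

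**What to change.** 1. In the sample size paragraph, correct or delete the sentence claiming that 120 patients are needed. State the two rates, alpha, sidedness, power and test actually used, and which difference is meant. Describe the size as feasibility-based only if the sponsor confirms that it was.
2. Add that, at two-sided 5%, 120 patients give about 6% power for 35% versus 30% and reach 80% only for about 35% versus 12%. If another level or sidedness is adopted, give the matching figures.
3. Optional: under Statistical Issues, report the mortality risk difference with a 95% confidence interval (about ±17 points by the Wald method). State that non-significance alone does not rule out a 5-point reduction, and that larger effects are judged from the interval. Name the interval method and say which analysis decides, because the two can disagree. With 21 versus 11 deaths, Fisher p = 0.062 while the Wald interval is 1.1 to 32.2 points and excludes zero.

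Items 1 and 2 cost a few sentences. Item 3 adds one interval and a short explanation. No extra patients are asked for, and the power itself is unchanged.
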